NCT04236245

VENCLOSE CLINICAL PROTOCOL VENC17A

Document Title: EU Post Market Clinical Follow-Up Study of the Venclose System for Saphenous Vein Incompetence

Venclose[™] Clinical Protocol VENC17A

EU Post Market Clinical Follow-Up Study of the Venclose System for Saphenous Vein Incompetence

Investigator

[name] & [name] Venenzentrum am Bruehl [name] Germany [contact] [contact]

Sponsor

Venclose, Inc. [name]

Study Contact

[name], BS, MS, CCRA Vantage Clinical Advisors [contact] Email: [contact]

Revision Date: 07AUG2019

Document Title: EU Post Market Clinical Follow-Up Study of the Venclose System for Saphenous Vein Incompetence

PROTOCOL AGREEMENT PAGE

I, the Investigator, agree to:

- Assume responsibility for the proper conduct of the study and not to deviate from the procedures described in the protocol;
- Be thoroughly familiar with the procedures as described in the protocol and any other information sources provided by the Sponsor;
- Conduct the study in compliance with the protocol and all applicable regulatory requirements;
- Permit monitoring and auditing of the study by the Sponsor and/or representatives, and inspections by appropriate regulatory authority(ies); and
- Ensure that all persons assisting with the conduct of the study are properly qualified for their function.

Investigator Name (Print)

Investigator Signature

Date

Sponsor Name (Print)

Sponsor Signature

Date

Document Title: EU Post Market Clinical Follow-Up Study of the Venclose System for Saphenous Vein Incompetence

I PROTOCOL	2 SYNOPSIS
Protocol	VENC17A
Number	
Protocol Titlo	EU Post Market Clinical Follow-Up Study of the Venclose System for
	Saphenous Vein Incompetence
	Venclose, Inc.
Sponsor	[name]
Sponsor	[name]
	[name]
Study Type	Post Market Clinical Follow-up
	This is a prospective, non-randomized study in which patients who meet
	eligibility criteria and consent to participate will undergo a minimally
Study Design	invasive procedure using radiofrequency (RF) energy for ablation of the
	great sanhenous vein (GSV)
	great saphenous veni (05 v).
D	To confirm the safety and performance of the Venclose System for
Primary	radiofrequency segmental thermal ablation of incompetent Great
Objective	Saphenous Veins (GSVs).
Study Duration	Up to 3 months to enroll plus one year to complete follow-up
Participant	Twelve months post-procedure
Duration	
Study Site(s)	One study site located in Germany
Sample Size	Up to 25 subjects treated with the Venclose System
	Baseline Visit Treatment Visit Follow-Un Visits (3-day 3-month 6-
Study Visits	month and 1 year post procedure)
	month, and T year post procedure)
	1. Vein Occlusion Rate (percentage of limbs with occlusion of the treated
	vein) at 3-day, 3-month, 6-month, and 12-month Follow-up Visits.
Primary	
Endpoints	2. Reflux-free Rate (percentage of limbs without reflux, as determined by
	Duplex Ultrasound Scan) at 3-day, 3-month, 6-month, and 12-month
	Follow-up Visits.
Secondary	Clinical signs and symptoms of lower limb venous disease at baseline 2
Endnointe	months 6 months and 12 months as measured by
Enupoints	monuis, o monuis, and 12 monuis as measured by:

1 PROTOCOL SYNOPSIS

Document Title: EU Post Market Clinical Follow-Up Study of the Venclose System for Saphenous Vein Incompetence

	1. Clinical Etiologic Anatomic Pathophysiologic (CEAP) Classification;				
	2. Venous Clinical Severity Score (VCSS).				
	Side effects/adverse events after treatment through 12-month follow-up.				
	Inclusion Criteria				
Inclusion/ Exclusion Criteria	 Subject is male or female and 18 to 80 years old (inclusive) at time of enrollment (signing of consent). Subject has significant venous reflux by DUS, defined as reverse flow with reflux duration greater than 0.5 seconds after the Valsalva maneuver or distal augmentation while the patient is standing or in reverse Trendelenburg position. Subject is eligible for endovascular treatment, as determined by the treating investigator. Subject's general physical condition allows for a significant amount of ambulation after the procedure, as determined by the treating investigator. Subject is willing and able to complete study requirements, including all follow-up visits and assessments. Subject voluntarily provides written informed consent to participate in this study. 				
	Exclusion Criteria				
	 There is evidence of old or fresh thrombus in the subject's diseased vein segment to be treated, as determined by DUS within 2 weeks prior to the index procedure. In the judgment of the treating investigator heat energy delivery to the subject would be contraindicated. Subject is concurrently participating in another interventional clinical trial. Subject is pregnant or plans to be pregnant or lactating at the time of the treatment procedure. Subject has known or suspected allergies or contraindications to any general or local anesthetic agents and/or any antibiotic medication that cannot be adequately pre-treated. 				

Document Title: EU Post Market Clinical Follow-Up Study of the Venclose System for Saphenous Vein Incompetence

Table of Contents

PROTOCOL AGREEMENT PAGE	2

2 BACKGROUND AND OBJECTIVES

The primary objective of this Post-Market Clinical Follow-up (PMCF) prospective, nonrandomized study is to confirm the safety and performance of the CE-marked Venclose System for radiofrequency segmental thermal ablation of incompetent Great Saphenous Veins (GSVs).

These types of post-market studies are recommended by MEDDEV 2.12-2 rev 2 for all medical devices for which there is not medium- to long-term clinical evidence available at the time of gaining approval to market in the EU, and for medical devices that have relied on clinical data from equivalent devices for conformity with the Essential Requirements of the Medical Device Directive (MDD). It is hypothesized that the safety and performance of the Venclose System will be similar to the equivalent, alternative CE-marked ClosureFast System, which Venclose relied on for clinical data for conformity with the Essential Requirements.

The data and conclusions derived from this PMCF study will be used to provide additional data for updating the clinical evaluation in order to assess whether the device continues to comply with the Essential Requirements. Such an assessment may result in corrective or preventive actions, for example: changes to the labeling/instructions for use, changes to manufacturing processes, changes to the device design, or public health notifications.

This study has been designed in accordance with MEDDEV 2.12/2 rev 2.

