5 STUDY ENDPOINTS

5.1 PRIMARY ENDPOINTS

The primary study endpoints are percentage of limbs with vein occlusion in the treated vein and the absence of reflux in the treated vein, as determined by Duplex Ultrasound Scan (DUS).

Primary endpoint analysis will be accomplished by measuring the treated vein recanalization and reflux rates at 3 days (+/- 2 days), 3-months (+/- 2 weeks), 6 months (+/- 3 weeks) and 12 months (+/- 4 weeks) post-procedure. Recanalization will be determined by DUS and clinical assessment during follow-up. A twelve-month follow-up is sufficient to assess a stable occlusion in the treated vein, as it is the typical final follow-up time frame for varicose vein treatment when assessing technical and symptomatic recurrence.

Specific primary endpoint measurements will be:

 Vein Occlusion Rate – percentage of limbs with occlusion of the treated vein: Occlusion is defined as the absence of any flow from 3 cm inferior to the Saphenofemoral Junction (SFJ) along the entire length of the treated vein as documented on the post-procedure and follow-up DUS. The 3 cm limit was selected

Document Title: EU Post Market Clinical Follow-Up Study of the Venclose System for Saphenous Vein Incompetence

to represent the occlusion status of the proximal Great Saphenous Vein (GSV) and to allow precise evaluation with a typical 4 cm linear ultrasound probe. In line with the equivalent ClosureFast device clinical studies^{2,3} flow in the stump of the GSV up to 3 cm below the SFJ is considered normal and does not constitute a failure.

2) Reflux-Free Rate – percentage of limbs without reflux in the treated vein: Reflux is measured by Duplex Ultrasound imaging along the entire treated vein segment(s). Reflux is defined as reversal flow >0.5 seconds with subject standing or in reverse Trendelenburg position of at least 15° after distal augmentation.

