Although ClosureFast studies utilized the original 1996 CEAP and 2000 VCSS scales, the Venclose post-market study will utilize the official 2004 and 2010 revised version of the scales, respectively, for consistency with the current state-of-the-art of clinical assessment for endovascular coagulation of blood vessels in patients with superficial vein reflux. Comparison efforts between the Venclose and ClosureFast studies will focus on similar percentages of score reduction, and may include an analysis of the differences in scale composition, as needed.

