15 DATA ANALYSIS

Subject demographics will be reported using descriptive measures including count, percentage, mode, median or mean as appropriate for the level of measurement. Clinical outcomes and visit assessment data will be presented with frequency distributions and cross-tabulations with selected demographics or other study variables.

Endpoint analyses of CEAP classifications and VCSS scores will be performed on a persubject and/or per-limb basis for the 3-day, 3-, 6- and 12-month follow-up visits. Descriptive analyses of when desired outcomes were achieved will be calculated with sub-

Document Title: EU Post Market Clinical Follow-Up Study of the Venclose System for Saphenous Vein Incompetence

group comparisons as appropriate. Estimation methods may be used to report effect size along with confidence intervals for sub-group comparisons.

Any adjunctive procedures, adverse events or protocol deviations will be described and reported as required.

If a subject has had treatment and subsequently withdraws consent or is terminated/lost-tofollow-up, data gathered as part of the study protocol up to the date of consent withdrawal or termination may be utilized in the data analysis. The Informed Consent document makes clear to the subject that non-identifiable health data gathered as part of study activities before the date of consent withdrawal or termination may be utilized in the manner and with the protections described in the Consent document.

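### The stated aim is to confirm safety and performance, and Section 2 hypothesizes similarity to ClosureFast, but no benchmark, margin or primary-rate interval is planned, and the only comparison rule is undefined as worded for CEAP

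*Combined protocol and SAP*

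**What the plan says.** The synopsis (Section 1) gives the primary objective as "To confirm the safety and performance of the Venclose System for" ablation of incompetent great saphenous veins, and Section 2 repeats it. Section 2 alone goes further: "It is hypothesized that the safety and performance of the Venclose System will be similar to the equivalent, alternative CE-marked ClosureFast System".

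The design is single-arm and non-randomized at one site, with this sample size: "Up to 25 subjects treated with the Venclose System". No derivation is given.

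Section 5.1 defines the endpoints per limb: "The primary study endpoints are percentage of limbs with vein occlusion in the treated vein", together with absence of reflux. It describes the analysis in one line: "Primary endpoint analysis will be accomplished by measuring the treated vein recanalization and reflux rates", at four visits.

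Section 15 is descriptive: "Clinical outcomes and visit assessment data will be presented with frequency distributions" and cross-tabulations. It names endpoint analyses only for CEAP and VCSS. Its only mention of intervals is this: "Estimation methods may be used to report effect size along with confidence intervals for sub-group comparisons".

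The one rule for comparing with ClosureFast is in Section 5.2.1. A sentence beginning "Although ClosureFast studies utilized the original 1996 CEAP and 2000 VCSS scales" explains that this study uses the revised versions. The next says that comparison will look for like percentage reductions in score, with an analysis of how the scales differ left optional.

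**The concern.** Confirming performance, or finding it similar to another device, calls for something to judge the result against and a statement of uncertainty. The plan supplies neither for its primary endpoints.

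Section 20 requires a final report to the Notified Body whose conclusions are tied to the study's objective. Sections 2 and 16 feed those conclusions into the assessment of whether the device still meets the Essential Requirements. Followed as written, the plan would let the report call the objective confirmed, or the device similar, from observed percentages in at most 25 subjects. A reader would have no planned indication of how low the true rate might be. The only comparison that is described concerns secondary scales, and one of the two does not fit the rule as worded.

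**Working it through.** **1. The plan's own figure.** The only design figure is up to 25 treated subjects. No alpha, power, precision target, reference rate or margin is stated, so it can be neither reproduced nor refuted. The check is what 25 can show.

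**2. What the documents offer as a benchmark.**
- Section 4 describes closure rates for radiofrequency devices as high, without a number.
- Section 5.1 aligns the stump-flow definition with ClosureFast studies but quotes no rate from them.
- Appendix 1 gives some event frequencies (for example, deep vein thrombosis under 1 in 100 limbs) as a general literature guide for radiofrequency or laser ablation. They are not ClosureFast rates and are not made criteria.

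**3. Exact (Clopper-Pearson) 95% intervals, one limb per subject.** The lower limit L solves P(X ≥ x | n, L) = 0.025; the upper limit U solves P(X ≤ x | n, U) = 0.025.
- 25/25: L = 0.025^(1/25) = 0.863, so 86.3-100%.
- 24/25: L solves L^25 + 25·L^24·(1 − L) = 0.025, giving 0.796; U = 0.975^(1/25) = 0.999; so 79.6-99.9%.
- 23/25: 74.0-99.0%.
- 20/20, if only 20 are evaluable: L = 0.025^(1/20) = 0.832, so 83.2-100%.
- 0/25 adverse events of a given type: U = 1 − 0.025^(1/25) = 0.137, so up to 13.7%.

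**4. Illustration of a similarity test.** The benchmarks of 90, 93, 95 and 97% and the 10-point margin are assumptions; none is in the documents. Similarity is declared if the one-sided 0.025 lower limit exceeds benchmark minus margin, and the true rate is set equal to the benchmark.
- 24/25 never suffices: its lower limit of 79.6% is below even the lowest threshold, 90 − 10 = 80%.
- 25/25 suffices at 90, 93 and 95%, because 86.3% exceeds 80, 83 and 85%. It fails at 97%, because 86.3% is below 87%.
- The chance of 25/25 is benchmark^25: 0.90^25 = 0.072, 0.93^25 = 0.163, 0.95^25 = 0.277. At 97% the chance of success is 0.

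The range is 0-28%.

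**5. The Section 5.2.1 rule.** Percentage reduction is 100 × (baseline − follow-up) / baseline, which needs a numeric score.
- VCSS is a total from 0 to 30, so it can be computed whenever the baseline exceeds 0. The two studies would, however, be using the 2000 and 2010 versions.
- CEAP is a set of ordered classes, C0 to C6 with C4 split into C4a and C4b, and no total is defined. A move from C4b to C4a has no percentage.
- A paired mean VCSS change in 25 patients has a 95% half-width of t(0.975, 24)/√25 = 0.413 SD.

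**6. Limbs and patients.** Section 7.3 analyzes the two limbs of a bilateral patient separately and gives no method for their correlation. Suppose, hypothetically, that all 25 patients were bilateral and one limb failed. Treating limbs as independent gives 49/50 = 98.0% (89.4-99.9%). The per-patient rate, requiring all treated limbs occluded, is 24/25 = 96.0% (79.6-99.9%). The documents give no bilateral count, so this shows only that the unit of the interval must be fixed.

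**The case against.** A descriptive single-arm post-market study needs no formal test, and this one claims none. The results are additional evidence for a wider clinical evaluation. Section 15 does not forbid intervals on the primary rates. Counts will be tabulated, so exact intervals could be added later without loss of data. Section 15's cross-tabulations would allow a CEAP shift table, and Section 5.2.1 openly discloses the version difference.

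Most of this stands, and it makes the defect one of wording and reporting rather than of design. It does not close the gap: an interval that may be added after the results are known is not planned, and the confirm and similar wording remains.

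Four stronger readings are tempting and should not be drawn:
- *Section 1 also hypothesizes similarity.* It does not; only Section 2 does.
- *The documents contain no reference rates at all.* Appendix 1 has some, though not for the primary endpoints and not as comparison criteria.
- *The comparison rule cannot work for CEAP.* It could mean the share of patients whose class falls, which is computable. The text does not say so, so the rule is undefined rather than impossible.
- *The study is too small and needs a particular larger number.* Without a reference and margin, no sample size follows. With the same assumed benchmarks and a 20-point margin, the chance with 25 limbs would be 54-83%.

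**Conclusion.** The concern holds as a mismatch between aim and plan. The primary rates have no benchmark, margin or planned interval, the safety comparison has no designated reference, and the sole comparison rule is confined to secondary scales, is undefined as worded for CEAP and crosses VCSS versions.

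The firm size is the precision. Even a perfect 25/25 leaves the lower limit at 86.3%, one failure lowers it to 79.6%, and zero events of a type leaves up to 13.7%. These figures assume 25 evaluable subjects with one limb each. The 0-28% chance of showing similarity is illustrative and rests entirely on the assumed benchmarks and 10-point margin. Nothing here shows that the device is dissimilar to ClosureFast or that the sample size is wrong for a descriptive study. This should be corrected before the final report is written.

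**What to change.** 1. **Sections 1 and 2.** Restate the objective as estimating safety and performance with 95% confidence intervals. State in Section 2 that no formal conclusion of similarity to ClosureFast will be drawn.
2. **Section 15.**
   - Report the occlusion and reflux-free rates per limb at each visit with the number evaluable, keeping the Section 5.1 definitions.
   - Beside them, report a per-patient rate (all treated limbs occluded, or all reflux-free) with an exact Clopper-Pearson 95% interval, labelled as per-patient.
   - Include in the per-patient rate only patients with every treated limb assessed at that visit, whatever the result. Report how many are excluded and any failures among them. Keeping partly assessed patients only when a limb has failed would bias the rate downward.
   - Any interval placed on the limb rate must allow for within-patient correlation.
   - Report per-patient adverse event rates with exact 95% intervals.
3. **Section 5.2.1.** Replace percentage score reduction with a baseline-to-visit CEAP shift table and the paired mean VCSS change with 95% interval, one value per patient. Make no similarity claim across scale versions.

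The cost is wording in four sections, eight primary intervals (two rates at four visits), the adverse event and VCSS intervals, and the shift table, with no extra patients or data. The downside is a more modest claim, and an exact interval that belongs to the per-patient rate rather than to the limb rate defined as primary.

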3 TECHNOLOGY SUMMARY

The Venclose[™] Radiofrequency (RF) System (Generator and Catheters) is intended for use in endovascular coagulation of blood vessels in patients with superficial vein reflux. The Venclose System uses resistive radiofrequency ablation via bipolar energy delivery to heat the wall of an incompetent vein with temperature-controlled RF energy to cause irreversible luminal occlusion, followed by fibrosis and ultimately resorption of the vein. The blood then naturally reroutes to healthy veins.

The technique involves percutaneous access and insertion of the endovenous sectional radiofrequency (EVSRFTM) catheter into the target vein under ultrasound guidance and relies on the use of local anesthesia and thermal energy, from a radiofrequency generator, applied to the target vein. After each treatment, the EVSRF catheter is withdrawn a single length of the heating coil and another treatment is performed, until the entire vessel has been treated. This sectional treatment involves thermal damage that is inflicted upon the venous endothelium and into the wall, resulting in contraction and ultimately destruction of the vessel.

Document Title: EU Post Market Clinical Follow-Up Study of the Venclose System for Saphenous Vein Incompetence

The procedure can be performed in an outpatient setting, without the need for general anesthesia, allowing for a walk-in/walk-out procedure with minimal postoperative recovery time.

The Venclose System consists of two (2) main components: 1) The EVSRF Ablation catheter (model VC-10A2.5-6F-60, 60cm or VC-10A2.5-6F-100, 100cm) with integrated cable connector which, using sectional ablation, treats the vein in 10 cm or 2.5 cm segments, and 2) the Venclose digiRF generator (model VC-RFG-1) which delivers RF energy to the EVRSF catheter.

The Venclose System is comprised of the following accessories:

- Power cord for generator for the geographical region that the generator is sold
- Optional foot pedal (model VC-FP-1)

The following supplies are necessary for the procedure, but are not provided with the Venclose System:

- Duplex or B-mode ultrasound console
- Supplies for sterile procedure
- Tilt table (recommended)
- 6F introducer sheath, with matching dilator, guidewire and percutaneous access needle (access kit/ introducer kit)
- Local or general anesthesia
- Post-operative compression as recommended by physician

EVSRF catheters have a handle with logic circuitry and a button for starting treatment cycles. The generator is a 60-Watt multi-voltage (24V or 9V) power delivery system that uses digital radiofrequency at 460 kHz. The system will be used to perform endovenous ablations at 120°C for 20 seconds per cycle, matching a treatment protocol that has been widely studied over the last 10 years¹.

4 RISKS AND BENEFITS

Bipolar segmental radiofrequency ablation technology has years of history of clinical safety and effectiveness in humans in the delivery of radiofrequency energy to peripheral veins in the leg. Procedures utilizing radiofrequency ablation devices are associated with consistently high successful vein closure rates, with side effects that are low in frequency,

¹ Proebstle TM, Alm BJ, Gockeritz O, Wenzel C, Noppeney T, Lebard C, Sessa C, Creton D, Pichot O. Five-year results from the prospective European multicenter cohort study on radiofrequency segmental thermal ablation for incompetent great saphenous veins. *BJS* 2015; 102: 212-218.

Document Title: EU Post Market Clinical Follow-Up Study of the Venclose System for Saphenous Vein Incompetence

mostly minor/transient and common to catheter-based procedures in general. Radiofrequency ablation sessions are usually performed in an outpatient setting with local anesthetic and typically require no sedation. Patients are fully ambulatory following treatment, and the recovery time is short for the majority of patients.

Potential complications include, but are not limited to the following: vessel perforation, skin discoloration, nerve injury, phlebitis, hematoma, thrombosis, infection, skin burn and pulmonary embolism. Other adverse events are often related to and can be complicated by the progression of the underlying incurable and progressive nature of venous disease, the presence of co-morbid conditions, and/or the risks of tumescent anesthesia. Risks related to the use of catheters in general and thermal interventions in particular are considered to be manageable (minor, transient and treatable) when compared to the possible benefits of controlled and selective destruction of diseased peripheral vasculature. These risks may be minimized through adherence to the device instructions for use, proper patient selection and monitoring of the patient's status during treatment and follow-up. Radiofrequency ablation provides a minimally-invasive and outpatient-based treatment alternative for patients with varicose veins and peripheral venous insufficiency that is well-established and widely-used in the medical community.

The benefits of treatment with ablative radiofrequency energy include reduction in the overall severity of venous symptoms and improved quality-of-life with typically only mild postoperative discomfort.

